- If a subject discontinues prior to the Week 24 visit and has a Safety follow-up visit that extends beyond 24 weeks from the first study drug administration (ie, what would have been the Week 24 visit), then the period for TEAEs for that subject will end at 24 weeks

(160 days) from the first study drug administration for the interim analysis. Any TEAEs collected at the Safety follow-up visit occurring after the 24 week timepoint will be captured in the Final Clinical Study Report (CSR). This allows for a maximum treatment period of 24 weeks for each subject in this interim analysis.

- For subjects who complete the Week 52 visit, all AEs which started on or after the date of first dose of study medication and on or prior to the date of Week 50 administration of study medication + 70 days will be considered a TEAE for the final analysis summaries.
- For subjects who discontinue prior to the Week 52 visit, all AEs which started on or after the first dose of study medication and on or prior to the date of last administration of study medication + 70 days will be considered a TEAE for the final analysis summaries.
- For subjects who die prior to the Week 24/52 visit, all AEs which started on or after the first dose of study medication and prior to or on the date of death will be considered a TEAE for the interim/final analysis summaries.

The following AE summaries will be produced for the Combined Initial and Maintenance Periods considering just those AEs which emerged while on blinded or open-label treatment using the SS, PsAS and CSS:

- Incidence of TEAEs – Overview
- Incidence of TEAEs by TE-ADA status – Overview
- Incidence of TEAEs by TE-ADA status (Includes EAIR and EAER)
- Incidence of TEAEs by Maximum ADA Titer (Safety Set (Excluding PBO treatment group) and Cohort Safety Set combined)
- Incidence of TEAEs (includes EAIR and EAER)
- Incidence of Serious TEAEs (includes EAIR and EAER)
- Incidence of TEAEs Resulting in Permanent Discontinuation of Study Drug
- Incidence of TEAEs leading to death
- Incidence of TEAEs by Maximum Intensity
- Incidence of TEAEs by Maximum Relationship
- Incidence of Serious TEAEs by Maximum Relationship
- Incidence of Non-serious TEAEs by Maximum Relationship
- Incidence of TEAEs on or above Reporting Threshold of 5% (not for CSS)
- Incidence of Non-serious TEAEs on or above Reporting Threshold of 5% (not for CSS)
- Incidence of Non-serious TEAEs on or above Reporting Threshold of 5% by Maximum Relationship (not for CSS)
- All AEOI tables

The following AE summaries will be produced for the Combined Initial and Maintenance Periods considering AEs which emerged while on blinded treatment only for the SS, PsAS:

- Incidence of TEAEs – Overview
- Incidence of TEAEs (includes EAIR and EAER)

- Incidence of Serious TEAEs (includes EAIR and EAER)
- Incidence of TEAEs Resulting in Permanent Discontinuation of Study Drug

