^a Urine dipstick to be performed every 2 months after Week 16. If blood or WBC are present, a microscopic examination should be performed.

^b Pregnancy testing will be serum testing at Screening, and urine at all other visits.

^c HBV DNA to be performed at Screening. If the subject is either hepatitis B surface antibody-positive or hepatitis B core antibody-positive at Screening, quantitative measurement of HBV-DNA should be performed every 4 weeks from Baseline to Week 52 and at SFU.

^d Subjects who are on escape treatments should have samples taken for plasma CZP concentration and anti-CZP antibodies at the time of escape from double-blind treatment and 10 weeks after the final study drug administration.

^e Includes evaluation of signs and symptoms of active TB and risk for exposure to TB.

^f Screening chest x-ray must have been performed within 3 months prior to the Screening Visit.

^g PASI, PGA, and BSA will not be performed for subjects with generalized pustular PSO. The Global Improvement Score, JDA Severity Index, and CGI-I will be performed for subjects with generalized pustular PSO. For subjects with erythrodermic PSO, the CGI-I will be performed. Note: The CGI-I and Global Improvement Score will not be performed at Screening or Baseline.

^h For subjects with psoriatic nail disease only

[figure not shown]
ⁱ Only for chronic plaque PSO subjects with PsA: HAQ-DI, Patient’s Assessment of Arthritis Pain (VAS), and PGADA (VAS)

^j Only for chronic plaque PSO subjects with PsA: swollen and tender joint counts and PhGADA (VAS)

^k Adverse events should be reported only if they occur after signing the Informed Consent form.

^l IMP administration of the IMP will occur after all other visit assessments have been completed.

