9.3 Relationship between immunogenicity and pharmacokinetics

The results of the interim analysis demonstrated that almost all subjects showed TE-ADA positivity regardless of treatments and psoriatic subgroups and the relationship between immunogenicity and pharmacokinetics could not be investigated sufficiently using the summaries of CZP plasma concentrations by TE-ADA status. The subjects who had TE-ADA positivity showed various ADA titer values, therefore, the relationship between immunogenicity and pharmacokinetics will be investigated using the ADA titer values.

A scatter plot will be prepared between CZP concentrations (Y-axis) versus ADA titers (X-axis) until Week 16 without baseline and SFU for combined PK-PPS and CPKS. The X-axis will present the logarithm of the ADA titer to base 2. Symbols will present the treatment groups.

Maximum ADA titers until Week 16 or Week 52 will be derived by subject. For the derivation of maximum ADA titers, a missing ADA titer value will be imputed by 0.5 when the sample was negative.

A scatter plot will be prepared between dose-normalized CZP concentrations at Week 16 (concentration/dose, either 200 or 400; Y-axis) versus maximum ADA titers (X-axis) until Week 16 without baseline and SFU for combined PK-PPS and CPKS. The X-axis will present the logarithm of the maximum ADA titer to base 2.

A box plot will be prepared between dose-normalized CZP concentrations at Week 16 (concentration/dose; Y-axis) versus maximum ADA titers (X-axis) until Week 16 without baseline and SFU for combined PK-PPS and CPKS. The X-axis will present the logarithm of the maximum ADA titer to base 2.

Based on the maximum ADA titers, subjects will be categorized into the following subgroups:

- Low: maximum ADA titer ≤ 1024
- High: maximum ADA titer > 1024

For the Initial Period or the Combined Initial and Maintenance Period, the maximum ADA titers until Week 16 or Week 52, respectively, will be used for the categorization.

CZP plasma concentration data will be tabulated and summarized by treatment group and visit and by maximum ADA titer category within the treatment group using the geometric mean, geometric coefficient of variation, geometric mean 95% confidence interval (CI), median, minimum and maximum. For each treatment group, geometric mean plasma concentration time curves will be plotted by maximum ADA titer category.

Initial Period

Summaries based on PK-PPS will be presented for the following treatment groups:

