If the month and year of first dose in the Maintenance Period is the same as the month and year of onset, then use the date of first dose in the Maintenance Period.

If the month and year of onset is after the month and year of first dose in the Maintenance Period, then use the 1st of the month.

If the intensity of an adverse event is unknown, it is considered as severe.

If the relationship to study drug is missing, it is considered as related.

Subject time at risk represents the time a subject was at risk for having an AE. The definitions for subject time at risk (in days) for the Initial Period, Maintenance Period, and Combined Initial and Maintenance Period are outlined in [Section 10.1](#). These definitions will be used for

exposure-adjusted AE summaries. Selected AE summaries will include the exposure adjusted incidence rate (EAIR) with associated 95% confidence interval and the exposure adjusted event rate (EAER).

For EAIR, the numerator will be the total number of subjects experiencing the AE. The denominator will be 100 subject-years; that is, the total summation of individual subject-years at risk up to the first occurrence of the AE for subjects with that AE, and the total subject-years at risk for those subjects not experiencing that AE, divided by 100. EAIRs will be presented with a 95% exact confidence interval based upon the Chi-Square distribution (Ulm, 1990).

For EAERs, the numerator will be the number of AEs including repeat occurrences in individual subjects; the denominator will be 100 subject-years. That is, the total summation of individual subject-years at risk divided by 100. No confidence interval will be computed for EAER.

Presentation Conventions

The frequency of all TEAEs during the study period will be presented by treatment group and period separately by SOC, High Level Term (HLT), and preferred term (PT). The data will be displayed as number of subjects experiencing the AE, percentage of subjects, and number of AEs, sorted by descending frequencies of PTs in the 'All CZP Subjects' column and ordered alphabetically for SOC, HLT and identical frequencies for PTs.

Tables for the Incidence of TEAEs – Overview and Incidence of TEAEs will be generated by TE-ADA status using the following categories:

1. TEAEs starting before 1st anti-CZP antibody positive
2. TEAE starting on or after 1st anti-CZP antibody positive
3. TEAEs for subjects who are always anti-CZP antibody negative

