Each event will be classified according to whether it occurred on or after the first + result, or for a subject that remained negative throughout. Summaries will include the number of AEs, number of subjects with AEs and percentage of subjects with AEs, incidence rate with 95% CI, and exposure-adjusted event rate. For these summaries, a subject's associated time at risk will be split into the time before the first positive result, and on or after the first positive result. If a subject has multiple reports of the same AE (ie, those which code to the same PT) emerging both prior to first TE-ADA positive result and after first TE-ADA positive result, both events will be summarized in the table in the appropriate column.

Tables for the incidence of TEAEs will be generated for Combined Initial and Maintenance Period by maximum ADA titers using the following categories:

- Low: maximum ADA titer \leq 1024
- High: maximum ADA titer $>$ 1024
- NA: Since ADA titer for escape subjects is measured only at the time of transition and SFU, AEs emerging after escape transition will be included in "NA".

Since this tabulation covers all subjects assigned to CZP, AEs emerging while on PBO are excluded. Also, in order to include all CZP-treated subjects, subjects in the SS and the CSS will be combined together into a single table.

Finally, AEs of interest (AEOIs) will be evaluated as described below:

- Serious infections, including opportunistic infections. Serious infections will be summarized using the previously described “Any SAE” table. In addition, opportunistic infections (including tuberculosis) will be presented in a table using UCB-defined search criteria.
- Malignancies, including lymphoma. These will be presented in 2 tables using the criteria SMQ = “Malignant or unspecified tumours (SMQ)” and SMQ = “Malignant tumours (SMQ)”, respectively. The SMQ search will include terms in the Scope=Narrow group only. Note that the events include in the “Malignant tumours” table will be a subset of the events included in the “Malignant or unspecified tumours” table.
- Congestive heart failure. These will be manually identified by the study physician from the previously described Any TEAE table. No separate table is planned. In addition, serious cardiovascular events will be presented in a table using UCB-defined search criteria.

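### The Combined Period adverse event tables by TE-ADA status have no place for post-escape time, when antibodies are not sampled, so a completing placebo escaper's CZP time is filed as not positive by construction

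*SAP*

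**What the plan says.** SAP 10.2 (Presentation Conventions) sorts adverse events in the TE-ADA tables into three groups: starting before the first positive antibody result, starting on or after it, and "TEAEs for subjects who are always anti-CZP antibody negative". Exposure is divided in the same way: a subject's "associated time at risk will be split into the time before the first positive result, and on or after the first positive result". There is no group for unknown status.

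The same section lists these tables, with exposure-adjusted incidence and event rates, for the Initial Period and again for the Combined Initial and Maintenance Period. The Combined Period list covers events on blinded or open-label treatment, so escape exposure is in scope.

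On sampling, footnote d of Protocol Table 5-1 (repeated in SAP Table 13-1) has escapers sampled for CZP concentration and "anti-CZP antibodies at the time of escape from double-blind treatment and 10 weeks after the final study drug administration". SAP 9.2.3 makes the escape sample the antibody baseline for subjects randomized to placebo.

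For the neighbouring table by maximum ADA titer, SAP 10.2 recognizes the gap. Its reason is "Since ADA titer for escape subjects is measured only at the time of transition and SFU", and its rule is that "AEs emerging after escape transition will be included in" an NA category. No such rule is given for the TE-ADA tables.

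**The concern.** The split needs an antibody result to move a subject from one side to the other. Between escape and SFU no result is scheduled, and SFU falls at about the point where the adverse event window closes. For a placebo escaper, the first sample that can be treatment-emergent positive comes when there is almost no time at risk left to classify. The table will nevertheless report that time as before first positive or always negative.

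SAP 9.3 reports that at the interim "almost all subjects showed TE-ADA positivity regardless of treatments". If escapers behave similarly, some of this time is antibody-positive exposure recorded as not positive. That would pull the before/after rate comparison towards no difference, which is the less cautious direction for a safety table. SAP 8 expects most placebo subjects to be switched to CZP, so few of them would be exempt.

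**Working it through.** The plan gives no figure on this point, so there is none to reproduce. The check is date arithmetic on the SAP's formulas, followed by an illustration.

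**1. Time at risk on CZP for a completing placebo escaper** (SAP 10.1.2: Week 50 dose − first open-label dose + 70 days)
- Escape at Week 16: 34 × 7 + 70 = 308 days
- Week 24: 26 × 7 + 70 = 252 days
- Week 32: 18 × 7 + 70 = 196 days
- Week 40: 10 × 7 + 70 = 140 days

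**2. Part that can fall on or after a positive SFU sample.** SFU is due at last dose + 70 days, window −3/+14 days (Protocol 8). Time at risk ends at last dose + 70 days. SFU on time or late leaves 0 days. SFU at its earliest leaves 3 days, so 305/308 = 99.0% (Week 16 escape) to 137/140 = 97.9% (Week 40 escape) is still 'before'. If SFU is negative, everything goes to 'always negative'.

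**3. Who else is affected.** CZP-randomized escapers still negative at escape have the same gap from escape onward. An escaper who withdraws may have a Withdrawal Visit sample. If that is taken at last dose + 14 days, up to 70 − 14 = 56 days could fall on or after it.

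**4. Illustration.** These assumptions are not from the documents:
- 12 to 20 of the 25 planned placebo subjects escape at Week 16, complete, and are all filed in 'before'.
- 100 CZP-randomized subjects do not escape and are at risk for 60 weeks (Week 50 + 10 weeks).
- Time to positivity is exponential with a median of 4 to 12 weeks, detected at the next scheduled sample (Weeks 2, 4, 6, 8, 12, 16, 24, 32, 40, 52, SFU).
- Never-positive subjects go to the third column.
- The true rate ratio R after positivity is 2.

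Escaper time: 12 × 308/365.25 = 10.1 subject-years; 20 × 308/365.25 = 16.9.

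'Before' time from CZP-randomized subjects: 14.0 subject-years (median 4 weeks) to 33.4 (median 12 weeks).

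Escaper share of the column: 10.1/(10.1 + 33.4) = 23% to 16.9/(16.9 + 14.0) = 55%.

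Write u for the truly pre-positive time in the 'before' column and w for the time already positive but not yet detected. Expected reported ratio = R ÷ [(u + R·w)/(u + w)].

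| Setting | u | w | (u + 2w)/(u + w) | Ratio |
|---|---|---|---|---|
| Median 4, no escaper time | 11.056 | 2.912 | 1.2085 | 1.65 |
| Median 12, no escaper time | 28.549 | 4.895 | 1.1464 | 1.74 |
| Median 4, 20 escapers | 13.267 | 17.566 | 1.5697 | 1.27 |
| Median 12, 12 escapers | 32.217 | 11.346 | 1.2605 | 1.59 |

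The escaper rows add each escaper's 44 weeks, with on average 5.77 (median 4) or 15.95 (median 12) weeks truly pre-positive. Conditioning strictly on positivity by SFU moves the last figure from 1.59 to 1.57.

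With R = 1 the ratio is 1 in every row. With R = 1.3 it falls from 1.22–1.25 to 1.11–1.21.

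**The case against.** The strongest reply is that little depends on this table. It is descriptive, with no test or decision rule. The Initial Period version has no escape time and six scheduled post-baseline samples; in the same set-up it gives about 1.65 to 1.70, so an uncontaminated before/after comparison is already planned. SAP 9.5 plays down the earlier immunogenicity summaries for safety because almost everyone became positive. The summary of SAP Amendment 2 says that titer categories substitute for TE-ADA status in the final analysis, and the titer table does deal with escapers. All of this stands and limits the weight of the point. It does not remove it, because current SAP 10.2 still lists the TE-ADA tables for the Combined Period beside the titer table.

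A reader might go further than the documents allow in three ways:
- *Every placebo escaper's whole CZP exposure is misfiled, whatever the antibodies do.* The early SFU window and the Withdrawal Visit sample (Protocol 8.30, SAP 9.2.1) are exceptions. So, possibly, is a placebo subject positive at or before escape. The category labels split on any anti-CZP positive, which would put that subject in 'on or after'; a later sentence of SAP 10.2 refers to the first TE-ADA positive, which would not, since escape is the baseline.
- *Most escaper time is truly antibody-positive.* The interim finding is about ever becoming positive, not when, and the interim included no escape-arm efficacy or safety analysis. The documents do not establish this.
- *The only time-resolved look at antibodies and safety is lost.* The Initial Period tables show otherwise.

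Conversely, the Protocol section 8 visit lists show samples at Weeks 24, 32, 40 and 52 without exempting escapers, which might suggest the gap does not exist. Footnote d sets a specific escaper schedule, and the SAP itself says escapers are measured only at transition and SFU.

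**Conclusion.** The concern holds for the Combined Period TE-ADA tables as written. For a placebo escaper who completes and is not antibody-positive by escape, 97.9% to 100% of CZP time at risk, with its events, is classed as not positive because no sample could show otherwise. CZP-randomized escapers negative at escape are affected from escape onward. The SAP recognizes the gap and handles it in one table but not in the one next to it.

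The size is illustrative. A fall in the expected ratio from 1.65–1.74 to 1.27–1.59 rests on the assumed escape numbers, time to positivity and doubled rate, and on every escaper being filed in 'before'. Escapers negative at SFU would go to the third column and leave the before/after ratio alone, and with no true effect nothing is distorted. The primary endpoint and the Initial Period tables are untouched. This is a worthwhile correction to a secondary descriptive table, not a threat to the trial's safety conclusions.

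**What to change.** In SAP 10.2, add an 'NA (not sampled after escape)' column to the Combined Period TE-ADA tables and put all post-escape events there, as the titer table does for adverse events. State that post-escape time at risk goes there too. If subjects already positive at or before escape are instead kept in 'on or after first positive', say that this departs from the titer rule and lets escape-phase time enter only that column.

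In either case use one definition of first positive, either any anti-CZP positive or TE-ADA positive, in both the category labels and the text.

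The alternative is to delete the Combined Period TE-ADA tables and rely on the titer table.

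The cost is a sentence or two and one column, with no new data. The downside is that escape-phase events no longer contribute to the before/after rates.

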- Demyelinating-like disorders. These will be presented in a stand-alone table which is based on the SMQ = “Demyelination”. The SMQ search should include all TEAEs which code to a PT included in Scope=Narrow group within the SMQ. TEAEs which code to a PT included in the Scope=Broad group within the SMQ should be excluded from the search.
- Aplastic anemia, pancytopenia, thrombocytopenia, neutropenia, and leucopenia. These will be presented in a table using the criteria SMQ = “Haematopoietic cytopenias (SMQ)” in the subset of SAEs. The SMQ search will include terms in the Scope=Narrow and Scope=Broad groups.
- Serious bleeding events. These will be presented in a table using the criteria SMQ = “Haemorrhage terms (excl laboratory terms) (SMQ)” in the subset of SAEs.
- Lupus and lupus-like illness. These will be manually identified by the study physician from the previously described Any TEAE table. No separate table is planned.
- Serious skin reactions (eg, Stevens-Johnson Syndrome, toxic epidermal necrosis, and erythema multiforme). These will be manually identified by the study physician from the previously described Any SAE table. No separate table is planned.

The tables for the AEOIs will include the incidence rate with associated 95% confidence interval, and the exposure adjusted event rate.

Will also be summarized:

- Hepatic events. They will be identified using the following 5 SMQs: “Cholestasis and jaundice of hepatic origin (SMQ)”; “Hepatic failure, fibrosis and cirrhosis and other liver damage-related conditions (SMQ)”; “Hepatitis, noninfectious (SMQ)”; “Liver-related investigations, signs and symptoms (SMQ)”; and “Liver-related coagulation and bleeding disturbances (SMQ)”.
- Hypersensitivity reactions and anaphylactic reactions. Hypersensitivity reactions will be identified as TEAEs that emerge on the same day or within one day after a study medication injection reaction was received which code to the following 10 PTs: “Administration site hypersensitivity”; “Documented hypersensitivity to administered product”; “Drug hypersensitivity”; “Hypersensitivity”; “Hypersensitivity vasculitis”; “Infusion site hypersensitivity”; “Injection site hypersensitivity”; “Medical device

hypersensitivity”; “Type II hypersensitivity”; “Type IV hypersensitivity reaction”. Anaphylactic reactions will be identified using UCB-defined search criteria.

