- Major Cardiovascular Events (MACEs). They will be identified using the following SMQs: “Central nervous system haemorrhages and cerebrovascular conditions (SMQ)”, which includes the 3 following sub SMQs: “Conditions associated with central nervous system haemorrhages and cerebrovascular accidents (SMQ)”, “Haemorrhagic central nervous system vascular conditions (SMQ)”, “Ischaemic central nervous system vascular conditions (SMQ)” except events coding to PT “Transient ischaemic attack”. All serious TEAEs which code to a PT included in the HLT “Ischaemic coronary artery disorders” except events coding to PT “Chest Pain” or “Chest discomfort” and all serious TEAEs which code to a PT included in any of the following HLTs: “Heart Failures NEC”, “Left Ventricular Failures”, or “Right Ventricular Failures” and which also code to the SOC of “Cardiac Disorders” as Primary SOC will be included.

AE Summaries by Period

All of the presentations described above will be presented for the Initial Period. Subsets of the presentations described above will be presented for the Maintenance Period and for the Combined Initial and Maintenance Period. Details for these summaries are described below.

Initial Period

Summaries for the Initial Period will be presented by randomized treatment group (PBO, CZP 200mg Q2W, CZP 400mg Q2W, All CZP) based on the SS, PsA Set and the CSS. For these summaries, treatment-emergence is defined as follows:

- For subjects who complete the Week 16 visit and continue to the Maintenance Period, all AEs which started on or after the date of first dose of study medication and on or prior to the date of the Week 16 administration of study medication will be considered a TEAE for these summaries. The only exception to this rule is for the following types of events:
 - Those which code to a HLT of “Injection Site Reactions”
 - Those which have been designated as an Injection Reaction on the AE CRF and do not code to an SOC of “Investigations”
 - Those which have been identified as a hypersensitivity reaction or an anaphylactic reaction

When any of these events occur on the date of treatment switch at Week 16, the AE will be attributed to the treatment initiated at Week 16.

- For subjects who discontinue on or prior to the Week 16 visit, all AEs which started on or after the first dose of study medication and on or prior to the date of last administration of study medication + 70 days will be considered a TEAE for the analysis summaries.

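### SAP 10.2 ties its hypersensitivity definition to an injection reaction where it must mean an injection; read literally, this narrows the summary and weakens a Week 16 attribution rule

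*SAP*

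**What the plan says.** The hypersensitivity bullet in SAP 10.2 gives a case definition with two conditions. The first is onset: "identified as TEAEs that emerge on the same day or within one day after a study". The sentence then names the anchor and the second condition: "medication injection reaction was received which code to the following 10 PTs". One timing rule covers the whole list, which includes "Type IV hypersensitivity reaction" and "Hypersensitivity vasculitis". Anaphylactic reactions are handled in the same bullet by a separate sponsor-defined search.

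Three other parts of SAP 10.2 bear on this:

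- **Where the summary appears.** Hypersensitivity is outside the list of adverse events of interest, among further events to be summarized. For the first 16 weeks a general sentence covers it: "All of the presentations described above will be presented for the Initial Period". The itemized lists for the Initial Period and for the combined period do not name it; each ends with "All AEOI tables".
- **Week 16 attribution.** An event on the Week 16 visit date goes to the initial treatment by default. There are three exceptions: injection site reactions by high level term; events flagged as an injection reaction on the case report form (unless coded to Investigations); and events identified as hypersensitivity or anaphylactic reactions. These go to the Week 16 treatment.
- **General tables.** "The frequency of all TEAEs during the study period will be presented by treatment group and period separately by SOC", and then by high level term and preferred term, with no limit on time since injection.

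**The concern.** The anchor makes no sense as written, and it is not harmless, because a programmer could implement it. Injection reaction is an existing flag on the adverse-event form, so the literal rule can be coded. It would turn a count of listed events close to dosing into a count of listed events close to a recorded injection reaction. Because the Week 16 exception uses the same definition, the slip could also move an event between treatments on the one day when the attribution rule matters.

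The second question is the window. Once the anchor is read as the injection, an event in a listed term that starts two or more days after dosing, and before the next dose, is not in the dedicated summary. The SAP does not label that summary as acute and gives no reason for the window. A reader could take it as the full count for the 10 terms.

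**Working it through.** **1. The plan's own figure.** The bullet says 10 preferred terms. There are three site terms (administration, infusion, injection), three named by agent (documented to administered product, drug, medical device), the unqualified term, vasculitis, Type II and Type IV: 3 + 3 + 1 + 1 + 1 + 1 = 10. The figure is reproduced.

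**2. The two readings of the anchor, side by side.** Take an event in a listed term with onset on a dosing day or the next day.

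| Situation | Anchor = injection | Anchor = injection reaction (literal) |
|---|---|---|
| Injection reaction recorded that day or the day before | Counted | Counted |
| No injection reaction recorded | Counted | Not counted |

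The readings differ in the second row. The literal reading makes the summary conditional on a different adverse-event designation.

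**3. Consequence at Week 16.** Take a listed-term event on the Week 16 dosing date.

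- Anchor = injection: the event meets the definition, the third exception applies, and it goes to the Week 16 treatment.
- Literal anchor, no recorded injection reaction: the definition is not met. The event falls back to the initial treatment unless it codes to the injection site reaction high level term, is itself flagged as an injection reaction, or is caught by the anaphylaxis search.

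Misattribution therefore needs both literal programming and the failure of every other exception. The number of such events cannot be derived. SAP 8 says most placebo subjects switch at or after Week 16, so even the number who change treatment on that date is not stated.

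**4. What the window covers once the anchor is corrected.** Inputs: dosing every 14 days (Protocol 7.2); Initial Period doses from Week 0 to Week 14 (SAP 7); window of the dosing day plus one day (SAP 10.2). Assume a subject dosed at every visit who continues to Maintenance.

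- Doses: 14/2 + 1 = 8
- Days admitted: 8 × 2 = 16
- Days from first dose to the day before the Week 16 dose: 16 × 7 = 112
- Coverage: 16/112 = 2/14 = 14.3%
- Days not admitted: 112 − 16 = 96, or 12 in each of 8 intervals

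The Initial Period rule counts events "on or prior to the date of the Week 16 administration of study medication will be considered a TEAE for these summaries". The Week 16 date is left out of the 112 days because, with the corrected anchor, a hypersensitivity event on that date belongs to the Week 16 treatment.

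**5. Comparison with neighbouring searches.** The hepatic, demyelination, cytopenia and major cardiovascular searches in the same section set no onset window relative to an injection. Nothing elsewhere in the SAP returns later-onset listed-term events to the hypersensitivity summary.

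**The case against.** The case on the other side is good on several counts.

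- **The slip has an obvious reading.** A sensible programmer would read injection. This stands as a reason to call the effect minor. It does not justify leaving the text, because the literal phrase matches a real data field and the rule is used twice.
- **The window may be intended.** The bullet is paired with anaphylaxis, the list contains site-of-administration terms, and the category sits beside injection site reactions in the Week 16 rule. All of this points to reactions related to administration. This stands: the window is not shown to be an error. At most, a label is missing.
- **The documents do not say when Type IV reactions or vasculitis begin.** This stands too. One can say that the window may miss some listed-term events, not that it does.
- **The events are reported elsewhere.** The Initial Period also has tables of serious events, discontinuations, maximum intensity and maximum relationship. SAP 3.2.2 derives days since the latest injection for adverse events. This stands.
- **No protocol commitment is missed.** Hypersensitivity is not an adverse event of interest in Protocol 12.1.1.3. This stands.
- **The interim report has been done.** SAP 9.3 cites its results, and SAP 4.3 provides for release of treatment codes to sponsor personnel at that point. This is a reason to make any change additive.

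A reader might infer that the plan hides delayed hypersensitivity, or that 86% (96/112) of such events are lost. The documents support neither. The percentage is a share of days, no event counts or onset distribution are given, and the events stay visible by term and arm. A reader might also infer bias against one arm, but the rule is identical in all of them.

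**Conclusion.** The anchor wording is wrong and should be corrected. It is one word in an operative definition that governs a safety summary and one attribution exception. The harm arises only if the text is programmed literally.

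The single short window is not an error. It leaves later-onset events in listed terms out of the dedicated summary, for which the only clear commitment is the general sentence about the Initial Period. Labelling that count and showing the unrestricted count beside it would be a cheap improvement.

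The size is minor: the rule is the same in every arm, and no efficacy result is touched. The 14% coverage figure assumes on-schedule dosing and does not measure harm. Neither the number of events outside the window nor the number at risk of Week 16 misattribution can be estimated from the documents.

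**What to change.** In SAP 10.2:

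1. Delete the word *reaction* after *injection* in the anchor, so that the clock starts at the injection. This is the correction.
2. As an improvement, keep the same-day or next-day count, label it as acute onset, and state that it continues to drive the Week 16 exception.
3. Add one row to that summary: all treatment-emergent events in the 10 listed terms, by treatment group, regardless of time since injection.

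The cost is one deleted word, a short clarifying sentence and one table row. No new data are needed, since onset relative to the latest injection is already derived. Because interim results are already known, the added row should be marked as a later addition and the same-day or next-day count left in place. The downside is that the broader row may include events unrelated to study drug.
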